8.1. Efficacy Assessments

8.1.1. Moderate and Severe COPD Exacerbations

Moderate exacerbations are defined per protocol as clinically significant exacerbations that require treatment with oral/systemic corticosteroids and/or antibiotics.

Severe exacerbations are defined per protocol as clinically significant exacerbations that require in-patient hospitalization (i.e., ≥ 24 hrs) or result in death.

The decision to treat moderate exacerbations should be corroborated by review of data from the daily symptoms eDiary to confirm that the exacerbation was associated with deterioration of symptoms.

For safety reasons alerts will be programmed into the eDiary to encourage the participant to contact the investigator if their COPD symptoms worsen. The site will also receive notification of the alert. An alert itself will not be classified as a moderate exacerbation unless it resulted in subsequent treatment for the worsening of symptoms meeting the definition above.

8.1.1.1. Guidelines for Identifying Symptom Defined COPD Exacerbations

The following are symptoms used to ascertain an exacerbation of COPD:

Worsening of two or more of the following major symptoms for at least two consecutive days:

- Dyspnea
- Sputum volume
- Sputum purulence (color)

OR

Worsening of any one major symptom together with any one of the following minor symptoms for at least two consecutive days:

- Sore throat
- Colds (nasal discharge and/or nasal congestion)
- Fever (oral temperature $>37.5^{\circ}\text{C}$) without other cause
- Increased cough
- Increased wheeze

Site staff will have access to a symptom summary report through a web-based portal. The symptoms summary report will indicate when symptoms meet the above criteria.

If a participant is determined to have an exacerbation it should be treated per protocol as described in Section [8.1.2](#)

8.1.2. Exacerbation Treatment

If in the opinion of the Investigator/treating physician, the exacerbation is severe enough to warrant the need for oral corticosteroids (with or without antibiotics) the following guidelines should be used.

- The duration of treatment with oral corticosteroids should be ≤ 14 days (dose and type according to local practice)
- The duration of treatment with oral corticosteroids should not exceed 14 days unless given approval by the Medical Monitor
- Any course of oral corticosteroids started within 7 days of finishing a previous course will be considered as treatment for a single exacerbation

If, in the opinion of the Investigator/treating physician, there is evidence of respiratory bacterial infection that warrants treatment with antibiotics the following guidelines should be followed:

- The duration of treatment with antibiotics should be 7 to 14 days (dose and type according to local practice). If first line antibiotic treatment fails and additional

antibiotics are used, the total duration of antibiotic treatment should not exceed 30 days unless given approval by the Medical Monitor.

- Any course of antibiotics started within 7 days of finishing a previous course will be considered as treatment for the original exacerbation (i.e. a single exacerbation).

Note: Use of antibiotics for the treatment of upper or lower respiratory tract infection is not considered a COPD exacerbation unless worsening of COPD symptoms are documented by the Investigator in the participant's medical notes.

All medications used for the treatment of exacerbations must be recorded in the source documents and the exacerbation page of the eCRF.

Exacerbations should not be recorded in the AE section of the eCRF unless they meet the definition of an SAE.

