6.5.2. Permitted Medications and Non-Drug Therapies

The **COPD medications** listed below are permitted during the treatment period while the participant is on IP. The requirements for study inclusion with regards to this medication list are described in detail by Study Inclusion Criterion 5:

- If taken as standard of care therapy prior to Visit 1 the following are permitted:
 - inhaled corticosteroids
 - inhaled long-acting muscarinic antagonists
 - inhaled long-acting beta₂-agonists
 - methylxanthines
 - phosphodiesterase-4 (PDE-4) inhibitor
 - oral corticosteroids (chronic use only)
 - leukotriene receptor antagonists (Singulair)
- Oral or injectable corticosteroids (short course ≤ 14 days) only for the short term treatment of COPD exacerbations and/or pneumonia
- Antibiotics (short course ≤ 14 days) for the short term treatment of COPD exacerbations and/or pneumonia
- Mucolytics such as acetylcysteine
- Long term oxygen therapy (LTOT). To be eligible to enter the study participants who are on LTOT must be using at a flow rate of ≤ 2 L/minute at rest over 24 hours. However, oxygen therapy may be adjusted as deemed medically necessary at any time during the study. Oxygen therapy must be captured on the concomitant medication page of the eCRF. Supplemental oxygen is recommended for patients who exhibit oxyhemoglobin desaturation with rest or exertion (*e.g.* SaO₂ $\leq 88\%$) while breathing room air.
- Maintenance phase of pulmonary rehabilitation treatment (participants **are not** allowed to initiate treatment during the study).
- Rescue medication for prn use *e.g.* salbutamol or ipratropium.

The following **non-COPD medications** are permitted during the study (for example):

- Medications for rhinitis (*e.g.* intranasal corticosteroids, antihistamines, cromolyn, nedocromil, nasal decongestants)

- Topical and ophthalmic corticosteroids
- Unplanned localized corticosteroid injections (e.g. intra-articular and epidural)
- Vaccinations (Influenza vaccine, Pneumonia vaccine, Shingles vaccine, etc). Administration of influenza and pneumonia vaccines should be considered based on clinical discretion of the Investigator and local/national guidelines. Vaccines will be captured on the concomitant medication pages of the eCRF
- Allergy immunotherapy
- Antibiotics for short-term treatment (≤ 14 days) of acute infections. Long term treatment with antibiotics is not allowed
- Systemic and ophthalmic beta-blockers
- Smoking cessation treatments

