6.5.3. Prohibited Medications and Non-Drug Therapies

Medications noted as part of exclusion criteria are prohibited for the duration of the treatment period.

Eligible participants are expected to continue their Baseline maintenance COPD medications during the run-in period and throughout the intervention period. Where spirometry is performed (See SoAs in Section 1.3.1 and Section 1.3.2), participants will refrain from taking their morning dose of their maintenance COPD medications until instructed to do so by clinic personnel.

Rescue medication (i.e. salbutamol or ipratropium) must also be withheld for at least 4 hours before visits when spirometry is performed (see SoA Section 1.3), and prior to reversibility testing at Visit 1.

COPD medications and non-drug therapies that are prohibited during the randomized phase of the study:

- Acute phase of pulmonary rehabilitation (at any time during the study including Run-in)
- Long term systemic antibiotic therapy (antibiotics used for ≤ 14 days for acute infections or for exacerbations or pneumonia are allowed).
- Monoclonal antibodies
- Chronic oral corticosteroids for non-COPD treatment

Note: Chronic macrolide therapy is permitted. Participants taking chronic macrolides at Visit 1 should continue the macrolide throughout the duration of the study.

- Experimental anti-inflammatory drugs (non-biologicals) or other investigational products (biologic or non-biologic) within either 30 days or five drug half-lives prior to Visit 1, whichever is longer.
- Other investigational products (participants must have not received investigational products for 1 months or 5 half-lives prior to Visit 1, whichever is longer)
- Radiation therapy is excluded for 12 months prior to Visit 1 and throughout the study

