6.3. Appendix 3 Exclusions from Per-Protocol Population

The per-protocol population includes all participants in the mITT who do not have protocol deviations that may significantly impact the interpretation of efficacy results.

Specifically, a participant will be excluded from the per-protocol population if meeting any of the following criteria that could significantly impact the interpretation of efficacy results:

Number	Exclusion Description
01	Informed consent never signed
02	Did not meet at least one of the following inclusion criteria (as numbered in the protocol) 
 1. Participant must be at least 40 years of age at Screening Visit 1 3. COPD Diagnosis: Documented history of COPD of at least 1 year in accordance with the definition by the American Thoracic Society/European Respiratory Society 7. Smoking status: Current or former cigarette smokers
03	Met at least one of the following exclusion criteria (as numbered in the protocol) 
 1. Asthma: Participants with a past history or concurrent diagnosis of asthma 2. Other respiratory disorders: The Investigator must judge that COPD is the primary diagnosis 4. Lung resection: Participants with lung volume reduction surgery within the 12 months prior to Screening Visit 1. 10. Eosinophilic Disease: Participants with other conditions that could lead to elevated Eosinophils 11. Parasitic Infection: Participants with a known, pre-existing parasitic infestation within 6 months prior to Screening Visit 1. 15. Previous mepolizumab studies: Participants who have received interventional product in previous mepolizumab studies 17. Investigational Medications: Participants who have received an investigational drug within 30 days of Visit 1, or within 5 drug half-lives of the investigational drug
04	Did not meet the following randomization inclusion criteria (as numbered in protocol) 
 1. Blood eosinophil count: Participants that do not have a historical blood eosinophil count that satisfies screening inclusion criterion 2 (Protocol Section 5.1) must have Screening Visit 1 blood eosinophil count ≥ 150 cells/μL.
05	Use of prohibited medication during the study ^[1]

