06	Occurrence of any one of the following treatment related deviations for ≥ 2 consecutive doses or ≥ 3 doses at any time during the study: 
 Received study treatment to which they were not randomized Study treatment not administered per protocol Expired study treatment administered

Number	Exclusion Description
	Use of study treatment impacted by a temperature excursion which was not reported or approved, or which was disapproved for further use
07	Participant/investigator is unblinded

[1] See Section 6.5.3 of protocol for prohibited medications.

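### Protocol 8.1.2 allows up to 30 days of antibiotics in total after first-line failure, but 6.5.2 and 6.5.3 stop at 14 days, so SAP per-protocol exclusion 05 could remove participants who were treated as directed (minor)

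*Protocol*

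**What the plan says.** **Treatment rule.** Protocol 8.1.2 gives the base rule first: "The duration of treatment with antibiotics should be 7 to 14 days (dose and type according to local practice". If the first-line antibiotic fails and others are added, it moves to a total: "the total duration of antibiotic treatment should not exceed 30 days unless given approval by the Medical Monitor". Protocol 8.1.1.1 sends sites to 8.1.2 for treating exacerbations.

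**Permitted and prohibited lists.** In its COPD list, Protocol 6.5.2 permits antibiotics up to "14 days) for the short term treatment of COPD exacerbations and/or pneumonia". Protocol 6.5.3 prohibits long-term systemic antibiotics, with a bracketed allowance that use up to "14 days for acute infections or for exacerbations or pneumonia are allowed". It separately permits chronic macrolides. Neither section mentions first-line failure or refers to 8.1.2.

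**Analysis.** SAP 6.3 lists as per-protocol exclusion 05 "Use of prohibited medication during the study", with the footnote "See Section 6.5.3 of protocol for prohibited medications". SAP 6.1.5 identifies prohibited-medication use, as an intercurrent event, from protocol-deviation records and has it confirmed by blinded clinical review. SAP 3 gives the per-protocol set a supplementary role for the primary endpoint and fixes exclusions before unblinding. SAP 4.2.1 handles prohibited medication by treatment policy in the primary estimand.

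**The concern.** A site can follow 8.1.2 and still go beyond the allowance in 6.5.3, which is the section that exclusion 05 points to. The participants who can be caught this way are those with an exacerbation whose first antibiotic failed. A moderate exacerbation is defined by treatment with corticosteroids and/or antibiotics, so the trigger for exclusion is itself a primary-endpoint event. If the share of exacerbations needing longer treatment is similar in the two arms, the arm with more exacerbations loses more participants, and those lost tend to be frequent exacerbators. A per-protocol set selected in this way is a poor check on the primary result. The descriptive count of prohibited-medication events could also be inflated by treatment that the protocol itself allows.

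**Working it through.** **1. The passages side by side**

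| Antibiotics for one exacerbation | Protocol 8.1.2 | Protocol 6.5.2 / 6.5.3 |
|---|---|---|
| Up to 14 days | within the rule | within the rule |
| 15 to 30 days in total, after first-line failure | within the rule | outside the 14-day allowance |
| Over 30 days | needs Medical Monitor approval | outside the 14-day allowance |

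The sections part company in the second row, and also in the third when approval is given. Section 8.1.2 also treats an antibiotic course begun within 7 days of the previous one as part of the same exacerbation, so a total across courses is a natural unit there.

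**2. The plan's own figure**

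Inputs from Protocol 9.2 and 9.2.1: placebo rate 1.7 per year, 23% reduction (rate ratio 0.77, so 1.7 × 0.77 = 1.309 on mepolizumab), dispersion k = 0.55, 52 weeks, two-sided 5%, 90% power.

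n per arm = (1.960 + 1.282)² × (1/1.7 + 1/1.309 + 2 × 0.55) / (ln 0.77)² = 10.507 × 2.452 / 0.0683, which rounds up to 378. That is 756 in total, and 756 / (1 − 0.055) = 800. Both match the protocol. The standard error of the log rate ratio is √(2.452/378) = 0.081. None of these figures depends on the antibiotic rule.

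**3. Illustrative size in the per-protocol set**

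Let q be the share of exacerbations treated with antibiotics for 15 to 30 days. The documents give no value, so q is assumed. It is taken as equal in both arms and independent across exacerbations, and anyone with at least one such exacerbation is assumed excluded. Under the gamma-Poisson model behind the negative binomial, with μ the expected count over one year:

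- proportion excluded = 1 − (1 + kqμ)^(−1/k)
- rate among those retained = (1 − q)μ / (1 + kqμ)
- per-protocol rate ratio = 0.77 × (1 + kq × 1.7) / (1 + kq × 1.309)

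For q = 5%: 0.77 × 1.04675 / 1.03600 = 0.778.

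| q (assumed) | Excluded, placebo | Excluded, mepolizumab | Per-protocol rate ratio |
|---|---|---|---|
| 1% | 1.7% | 1.3% | 0.772 |
| 2% | 3.3% | 2.6% | 0.773 |
| 5% | 8.0% | 6.2% | 0.778 |
| 10% | 15.0% | 11.9% | 0.785 |
| 20% | 26.8% | 21.7% | 0.799 |

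At q = 5% the shift is ln(0.778/0.770) = 0.010, about one-eighth of the standard error of 0.081. At q = 10% it is ln(0.785/0.770) = 0.019, about one-quarter.

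A lower rate with longer follow-up (1.3 per year over an assumed 1.25 years, so μ = 1.625 on placebo) gives the same ratios to three decimals: 0.778 at 5% and 0.785 at 10%. At 10% the placebo rate among those retained would be 1.30 × 0.9 / (1 + 0.55 × 0.10 × 1.625) = 1.07.

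With no treatment effect the two brackets in the ratio formula are equal, and the per-protocol ratio stays at 1.

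**The case against.** The best reply is that the conflict is one of reading. Section 8.1.2 itself starts from 7 to 14 days, and its 30 days is a total that applies only after first-line failure. If the 14 days in 6.5.2 is a limit per course, two courses can fit under both sections. Section 6.5.3 prohibits long-term therapy, and whether a second acute course counts as long-term is a judgement. That it admits chronic macrolides shows that it is not a mechanical 14-day cut. This reading is available and softens the conflict. It does not settle it, because 6.5.3 speaks of the time for which antibiotics are used, without saying per course, and writes in the macrolide exception but none for first-line failure.

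There are also safeguards. A reader might infer that the SAP flags the intercurrent event straight from 6.5.3. It does not: SAP 6.1.5 works from logged deviations and requires blinded clinical review, and only the footnote to exclusion 05 cites 6.5.3. The Study Deviations Rules Document named in SAP 6.1.3 may already deal with the case, but it is not available here. So exclusion is possible, not certain. Even so, the protocol and SAP give reviewers no rule for choosing between the two limits, and blinding to arm does not prevent selection on outcome.

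A reader might also cite the 6.5.2 sentence "Long term treatment with antibiotics is not allowed" as a direct ban on the longer treatment. It stands in the list of non-COPD medications, under acute infections, and does not govern exacerbations.

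Finally, outcome-related exclusion is a general weakness of per-protocol sets. That is true, but here part of it would come from treatment that the protocol allows.

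**Conclusion.** The sections are inconsistent as written and need to be reconciled. The consequence is minor. A reader might infer that the primary result is at risk, and the documents do not support that: the primary mITT analysis keeps these participants and their data under treatment policy, the per-protocol analysis carries no test in the hierarchy, and the intercurrent-event counts are descriptive.

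The effect on the per-protocol rate ratio cannot be computed from the documents. Under the stated assumptions it moves from 0.770 to about 0.772, 0.778 or 0.785 for q of 1%, 5% or 10%, which understates the benefit. These are upper figures for each q, because they assume that review clears nobody. The direction rests on q being equal in the two arms.

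**What to change.** 1. Reconcile Protocol 6.5.2, 6.5.3 and 8.1.2 into one rule on antibiotic duration for an exacerbation, stating whether it applies per course or in total, and cross-refer the sections. Which duration applies is the sponsor's clinical decision.
2. Before unblinding, state in SAP exclusion 05 and in the deviation rules that exacerbation treatment in line with the reconciled rule is not prohibited-medication use. State also how treatment already given under 8.1.2 is classified.
3. Apply the same statement when deviations are reviewed for the intercurrent-event summary.

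The cost is one protocol clarification and a line each in the SAP and the deviation rules. Sample size, alpha, power and the primary analysis do not change.

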8.1.3. Health Related Quality of Life Assessments

All Clinical Outcomes Assessment (COA) efficacy endpoint assessments completed at study visits will be completed using the eDiary. Participants will complete the following PROs at study visits where indicated in the Schedule of Assessments (Section 1.3). Clinician rated response to therapy will also be collected on the eDiary.

- The COPD Assessment Test
- The St. George's Respiratory Questionnaire for COPD Patients
- Patient Global rating of COPD severity and Global Rating of change in COPD
- Patient and Clinician rated response to therapy

8.1.3.1. COPD Assessment Test (CAT)

The CAT [Jones, 2009; Jones, 2012] is a short and simple patient completed questionnaire which has been developed for use in routine clinical practice to measure the health status of patients with COPD. The CAT is an 8-item questionnaire suitable for completion by all patients diagnosed with COPD. When completing the questionnaire, participants rate their experience on a 6-point scale, ranging from 0 (no impairment) to 5 (maximum impairment) with a scoring range of 0-40. Higher scores indicate greater disease impact.

The CAT should be completed in the clinic at each scheduled in clinic visit, before any other visit procedures, as indicated in the SoA (Section 1.3)

8.1.3.2. St. George's Respiratory Questionnaire for COPD patients (SGRQ-C)

The SGRQ-C is a 40-item patient questionnaire, designed to measure health impairment by addressing the frequency of respiratory symptoms (questions 1-7) and the patient's current state (questions 8-14). Higher scores indicate greater impairment of health. The SGRQ-C is derived from the original SGRQ, and produces scores equivalent to the SGRQ instrument [Meguro, 2007]. The SGRQ-C is designed for supervised self-administration which means that the participant should answer the questionnaire by themselves, but that site staff can provide support if required. It is appropriate to help

clarify a question but do not provide an answer. If participants have difficulty reading questions may be read out loud. The participant's response should not be challenged.

Participants must complete the questionnaire while in the clinic for their scheduled study visit. The SGRQ-C should be administered after CAT and before any other study procedures at Randomization (Visit 2) and at additional visits indicated in the Schedule of Assessment (Section 1.3).

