10.10.2. Study Procedures During COVID-19 Pandemic

During the special circumstances caused by the COVID-19 pandemic, sites should consider specific public health guidance, the impact of any travel restrictions implemented by local/regional health authorities and local institutions, and individual benefit /risk when considering the need for a participant to attend the site for a visit.

For the duration of these special circumstances, home healthcare visits (home visits and telemedicine visits; see below) may be implemented for scheduled visits from Visit 5 and onwards for participants unable to attend a site visit due to COVID-19 related restrictions. For such visits every effort should be made to adhere to protocol-specified assessments and procedures. Missing protocol data/visits due to COVID-19 should be noted in participant notes and recorded as a COVID-19 protocol deviation.

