All assessments from Visit 5 and onwards stated in the SoA tables in Section 1.3.1 and 1.3.2 can be performed through home healthcare with the exception of the Exit Visit, and the below procedures, which must be performed in clinic:

- Pre-bronchodilator spirometry;
- Clinician rated response to therapy; and
- Physical examinations

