4.3.2.2. Main Analytical Approach

Descriptive statistics by visit will be presented for the mITT population up to Week 104, regardless of treatment discontinuation. Responders will be summarized by visit up to Week 52 for the mITT and mITT2 populations, and by visit up to Week 104 for the Extended Treatment population.

Statistical Methodology Specification

Model Specification

- | |
|---|
| 
 • A logistic regression model will be used to compare the proportion of responders in the mepolizumab arm compared to placebo for the mITT and mITT2 populations. • The analysis model will include the following terms: |
|---|

Fixed Categorical:	Treatment group, smoking status, geographic region
Fixed Continuous:	Baseline score

 Participants with missing covariate information will be excluded from the analysis 	
Model Checking & Diagnostics	

 Models will be checked for issues with convergence. 	
Model Results Presentation	

 The number and percentage of participants identified as responders, non-responders and the number with missing data imputed due to experiencing a COVID-19 pandemic related intercurrent event of IP discontinuation or interruption of 2 or more consecutive doses of IP prior to Week 52 will be displayed by treatment group, the non-responder group will be further categorized to display the number of participants withdrawn early from the study before Week 52 and the number with missing visit data. The estimated odds ratio, 95% CI and p-value comparing treatments from the logistic regression models will be displayed. A forest plot of the estimated odds ratio and 95% CI for the comparison of treatment groups will be provided by visit. 	
Subgroup Analyses	
Separate exploratory subgroup analyses will be carried out as outlined in Section 4.10.1 .	

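### SGRQ-C must be completed in clinic although home healthcare permits it, 52-week participants have no home route at Week 52, and the SAP drops the protocol's COVID-19 exemption from non-response for a missed visit

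*Protocol*

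**What the plan says.** **Capture and location.** Protocol 8.1.3: "All Clinical Outcomes Assessment (COA) efficacy endpoint assessments completed at study visits will be completed using the eDiary". This is the device on which the participant records symptoms each evening. For SGRQ-C, 8.1.3.2 is firm: "Participants must complete the questionnaire while in the clinic for their scheduled study visit". For CAT, 8.1.3.1 is softer: "The CAT should be completed in the clinic at each scheduled in clinic visit, before any other visit procedures".

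**Home healthcare.** Protocol 10.10.2.1 says that the assessments from Visit 5 onwards "can be performed through home healthcare with the exception of the Exit Visit, and the below procedures, which must be performed in clinic": pre-bronchodilator spirometry, clinician-rated response and physical examination. Footnote y (first 52 weeks) and footnote j (Weeks 52 to 104) say the same. The scope is set in 10.10.2, where home visits "may be implemented for scheduled visits from Visit 5 and onwards for participants unable to attend a site visit due to COVID-19 related restrictions".

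**Week 52.** Under footnote w of the first schedule, Week 52 is the Exit Visit for 52-week participants, with no dose given. For extended participants Week 52 is V15 in the second schedule, which is not an Exit Visit; CAT, SGRQ-C and home healthcare are all marked there.

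**Missing Week 52 scores.** Protocol 9.4.1 counts a missing CAT or SGRQ value as non-response only when it is not associated with COVID-19 disruptions or restrictions on or before that visit. SAP 4.3.2.1 makes study withdrawals non-responders and imputes under missing at random only after COVID-related discontinuation of study product or interruption of two or more consecutive doses. SAP 4.3.2.2 then breaks the non-responder group down into "the number of participants withdrawn early from the study before Week 52 and the number with missing visit data". SAP 4.3.3 applies the same approach to SGRQ.

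**Rank.** CAT and SGRQ responders at Week 52 are steps 3 and 4 of six in the testing hierarchy (SAP 2.1).

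**The concern.** Three things do not fit together.

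1. At a home visit, 8.1.3.2 forbids an SGRQ-C that Appendix 10 and the footnotes permit. A site cannot follow both.
2. Under COVID-19 restrictions, access to the Week 52 questionnaires depends on the duration a participant consented to, although the endpoint is the same.
3. The participants who lose the home route at Week 52 are kept away by COVID-19 restrictions. Protocol 9.4.1 shields exactly this group from non-response; the SAP does not.

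At stake are two endpoints under Type I error control. Scoring avoidable missing values as non-response shrinks the difference between arms, and failure at step 3 or 4 ends formal testing of everything below it.

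**Working it through.** **Following one participant through the rules.** Take a 52-week participant still on study product who is kept from the Week 52 visit by COVID-19 restrictions.

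- Home route: none, because the visit is the Exit Visit. The same person, if extended, has a home route at V15 under footnote j, although 8.1.3.2 still says clinic for SGRQ-C.
- Protocol 9.4.1: the missing value is COVID-related, so it is not a non-response.
- SAP 4.3.2 and 4.3.3: no discontinuation or interruption has occurred. No dose is due at Week 52 for this person, so the missed visit cannot itself create an interruption. The value falls under missing visit data, inside the non-responder group.
- SAP Table 1 (section 4.12) records the changed handling of prohibited medication but not this narrowing. The pattern-mixture sensitivity analyses that Protocol 9.4.1 promises for the responder endpoints do not appear in SAP 4.3.2 to 4.3.4.

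**The plan's own figure.** The documents give no power for the responder endpoints. The only relevant figure is the primary-endpoint sample size, which supplies n. With placebo rate 1.7, 23% reduction, dispersion 0.55, one year, 90% power and two-sided 5%:

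n per arm = (1.960 + 1.282)² × [1/1.7 + 1/(1.7 × 0.77) + 2 × 0.55] / (ln 0.77)² = 377.2, rounded up to 378.

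Total 756; 756/0.945 = 800. The stated numbers reproduce, so 400 per arm is used below.

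**Illustration of the loss.** All of the following are assumptions: true response 40% on placebo and 48% on mepolizumab; a share f of participants is fixed-duration; 3–10% of those have Week 52 scores missing because of COVID-19 restrictions, equally in both arms, and are scored as non-responders. The overall missing share is m = f × (0.03 to 0.10), and each response rate p becomes p(1 − m).

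Power = Φ(d/SE − 1.96), where d = p₂ − p₁ and SE = √{[p₁(1 − p₁) + p₂(1 − p₂)]/400}.

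No missing scores: d = 0.080, SE = 0.0350, d/SE = 2.287, power 62.8%.

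| Fixed-duration share f | m | Rates after scoring | Difference (points) | Power |
|---|---|---|---|---|
| 25% | 0.75% | 39.7% vs 47.6% | 7.9 | 62.2% |
| 25% | 2.5% | 39.0% vs 46.8% | 7.8 | 60.9% |
| 50% | 1.5% | 39.4% vs 47.3% | 7.9 | 61.6% |
| 50% | 5.0% | 38.0% vs 45.6% | 7.6 | 58.9% |
| 100% | 3.0% | 38.8% vs 46.6% | 7.8 | 60.5% |
| 100% | 10.0% | 36.0% vs 43.2% | 7.2 | 55.1% |

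At 700 per arm, the permitted maximum, with f = 50%, power goes from 85.7% to 84.7–82.4%.

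**Unequal missingness** (assumed overall shares, same response rates). With 3% missing on placebo and 6% on mepolizumab, d = 0.48 × 0.94 − 0.40 × 0.97 = 0.063. With the shares reversed, d = 0.48 × 0.97 − 0.40 × 0.94 = 0.090. The true difference is 0.080, so bias can run either way.

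**The case against.** A reader might infer that any 52-week participant who cannot travel to Week 52 becomes a non-responder on both endpoints. The documents do not support that, for five reasons.

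- **Scope.** Home healthcare is for COVID-19 restrictions only. Someone absent for another reason has no such route at any visit in either cohort, so the Exit Visit exclusion changes nothing for them.
- **CAT.** Its wording is a recommendation tied to in-clinic visits and does not forbid completion at a home visit. The direct contradiction covers SGRQ-C alone. CAT is still affected at Week 52, because the whole Exit Visit is excluded.
- **Source of the penalty.** Protocol 9.4.1 exempts COVID-related missing values. The penalty comes only from the SAP, and for a missed visit without withdrawal it rests on a description of a results display; the endpoint definition names only withdrawals.
- **Other routes out.** A participant with an earlier COVID-related discontinuation or interruption is imputed. A late visit may also count, because SAP 6.2.5.1 keeps out-of-window assessments under the nominal visit. SAP 6.2.2.1 caps the efficacy period at Day 372 for 52-week participants, and the two rules are not reconciled.
- **Reason for clinic completion.** Protocol 8.1.3.2 describes SGRQ-C as designed for supervised self-administration, so home completion changes the setting of a ranked endpoint.

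The first four narrow the point to COVID-19 restrictions and to the SAP rule, and that narrowing stands. The last is a fair caution but does not defeat the remedy: footnote j already accepts these questionnaires at home at V15, staff support is needed only if the participant asks for it, and it can be given by phone.

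**Conclusion.** The point holds within these limits. SGRQ-C has contradictory location rules at home visits. Under COVID-19 restrictions, 52-week participants lack the Week 52 home route that extended participants have. The SAP narrows the protocol's exemption from non-response without recording it as a change.

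The expected effect is modest dilution at steps 3 and 4, since the rule applies to both arms; bias arises only if missingness differs by arm. Under the assumptions above, power falls from 63% to about 62–59% if half of participants are fixed-duration. A drop to 60–55% might be inferred for the trial as a whole, but that requires every participant to be fixed-duration, and the documents do not give that share. The response rates and missed-visit rates are also not in the documents, so the figures show scale only. The contradiction and the protocol–SAP mismatch do not depend on them.

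**What to change.** 1. **Protocol 8.1.3.1, 8.1.3.2, footnotes y and j, and Appendix 10.** State that when a scheduled visit with CAT and SGRQ-C, including the Exit Visit, cannot be attended because of COVID-19 restrictions, the participant completes CAT and then SGRQ-C at home on the eDiary, with site staff available by phone. Record the place of completion. All other Exit Visit procedures stay in clinic.
2. **SAP 4.3.2 and 4.3.3.** Align with Protocol 9.4.1, so that a Week 52 value missing because of COVID-19 restrictions is imputed and not counted as non-response, whether or not doses were missed. If the narrower rule is intended, list it in SAP Table 1 with a reason.

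The cost is protocol and SAP wording and an eDiary prompt. A few SGRQ-C forms would be completed with remote instead of in-person support; the recorded location lets that be examined. The change does not recover scores from participants who withdraw or do not complete the forms.
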